Given the critical and urgent need to improve models of care for pediatric TB that include strengthened case finding and use of innovative diagnostics and drugs that may offer improved outcomes for children with TB infection or disease, The Elizabeth Glaser Pediatric AIDS Foundation (EGPAF) is implementing the Unitaid-funded Catalyzing Pediatric TB Innovation (CaP TB) project. CaP TB will develop and implement innovative models of care and accelerate the broad introduction of WHO-recommended and quality-assured drugs and diagnostics that will help bring care closer to children living with and at risk for TB and close the pediatric TB gap.

This protocol describes the program evaluation that will help to document the outcomes of the CaP TB project.

II. Project Goals and Objectives

A. Goal

To evaluate the effectiveness of the CaP TB project across ten countries on key service delivery and clinical outcomes and compare these outcomes to those obtained at baseline.

B. Objectives

1. Primary Objective

1. To evaluate the below TB service indicators and clinical outcomes for children 0-14 in facilities implementing the CaP TB project:
2. To evaluate the below TB service indicators and clinical outcomes for children 0-14 in facilities implementing the CaP TB project:
 - a. Number and proportion of children screened for TB among clinic attendees
 - b. Number and proportion of presumptive TB cases identified among children screened for TB
 - c. Number and proportion of presumptive TB cases referred for lab-based TB diagnosis
 - d. Number and proportion of pediatric presumptive TB cases who are tested with Xpert
 - e. Number and proportion of pediatric TB cases diagnosed with active TB among presumptive pediatric TB cases.
 - f. Number and proportion of presumptive TB cases identified among children screened for TB
 - g. Time between when a child is identified as a presumptive TB case and when the child is diagnosed with TB
 - h. Number and proportion of pediatric TB cases started on DS-TB treatment
 - i. Time between when a child is identified as a presumptive TB case and when the child is initiated on TB treatment
 - j. Number and proportion of pediatric DS-TB cases or cases treated with first-line TB treatment who achieve treatment success
 - k. Number and proportion of all TB index cases for whom successful contact tracing has been done
 - l. Number and proportion of pediatric household contacts who are negative to TB screening

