- Screening for TB (clinical symptoms or signs)
- Receiving services (such as contact tracing) as a result of being a contact of a TB index case
- Clinical diagnostic assessment for TB
- Microbiologic diagnostic assessment for TB
- Treatment for active TB
- TB preventive therapy

Data collection of pre-intervention baseline data will take place prior to the start of CapTB interventions or immediately after, ensuring that the calculated data abstraction period does not overlap with any of the early project interventions. Data collection in each site may last up to 4 days and in some cases data collection may last several days longer.

VI. Evaluation Design and Methods

CaP TB implementation data will be collected by project-specific data collection tools and/or from existing registers. Whenever possible, the CaP TB data collection will use existing site level data collection tools to gather the data for the project. However, where such tools do not exist or the tools have gaps to capture all the necessary indicators, we will introduce project-specific data collection tools, the Pediatric TB Intensified Case Finding Screening Tool (ICF tool), the CaP TB Pediatric TB Form and any other form that may evolve as we learn lessons from project implementation.

Use of project-specific data collection tools

As part of the CaP TB intervention, healthcare workers will fill out a Pediatric TB Intensified Case Finding Screening Tool (ICF tool). This tool has no identifying information and will provide information on 1) number of children screened for TB in each healthcare entry point (e.g. pediatric ward, outpatient department, MNCH clinic, and nutrition clinic); 2) sex of the child; 3) age of the child; 4) if the child has any signs of symptoms concerning for TB (according to WHO guidance); 5) if the child is a contact of a TB case; and 6) the date of screening. The forms are also color coded according to the healthcare entry points where children are seen (White= MCH/PMTCT; Blue= outpatient department; Pink= Nutrition; Yellow= Pediatric Ward, Other=to be decided). See Attachment: Pediatric TB Intensified Case Finding Screening Tool.

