For children with presumptive TB: For all patients with a positive TB screen (children who have signs and symptoms concerning for TB according to the left side of the ICF tool), or for children who are a household contact of a TB case, the CaP TB Pediatric TB Form will be used to collect data on TB clinical and bacteriological investigations, as well as treatment initiation information at patient level. In addition, this form will be used directly to screen for TB symptoms in HIV clinics and during screening of contacts of TB index cases in the community, instead of the ICF tool for those 2 entry points, in effort to minimize unnecessary duplication of data entry. This CaP TB Pediatric TB Form will be adapted to country-specific requirements in collaboration with the MOH. This form will be printed on quadruplicate carbonated multi-colored papers (See Attachment C: CapTB Pediatric Form).

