Data collectors will also collect the ICF tools from the various entry points and collate aggregated data using an ICF data abstraction tool (Attachment B: Pediatric TB Intensified Case Finding Screening Data Abstraction Tool) which will be entered directly into the electronic data entry form. Data collectors will also extract information, such as date of treatment completion, from the TB treatment and TB preventive therapy registers. In the pilot phase (years 1 and 2), data collectors will visit sites frequently for data extraction (approximately every 4-6 weeks). In the expansion phase (years 3 and 4), data collectors will visit sites less frequently for data extraction (approximately every 1-3 months).

Data collection when the project-specific data collection tools are not used

If the CaP TB Pediatric TB Form is not completed or the country does not support use of the ICF Tool and/or CaP TB Pediatric TB Form for all or part of the data collection, data collectors will extract data from relevant sources such as existing registers and logs as in the pre-intervention baseline data collection phase. An indicator mapping exercise will first be conducted to identify the location and source of all required data. This indicator mapping exercise is expected to inform the data collection process which will take place on site, at the project facility. Data will be extracted from the source register or log and, recorded in the baseline data abstraction tool and entered into the CaP TB Database Entry Tool developed for pre-and post-intervention data. Only data required for the project M&E activities will be extracted and will be the same data collected through the CaP TB Pediatric TB Form. EGPAF will closely monitor data collection activities of any country team that cannot use the CaP TB Pediatric TB Form to ensure high quality data is collected. All data collection tools and processes will be approved by the in-country IRB.

A. [Table 1. Indicator Outcomes and Data Sources](#)

This table presents an example of data sources. Specific data sources may vary from country to country. All country-specific data sources will be approved for data extraction by the local IRB.

Primary Outcomes	Data Source Pre-Intervention	Data Source Post-Intervention

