Number and proportion of children screened for TB among clinic attendees	TB screening logbooks/registers	Pediatric TB Intensified Case Finding Screening Tools and Clinic attendance registers And/or TB screening logbooks/registers
Number and proportion of presumptive pediatric TB cases identified among children screened for TB	TB screening logbooks/registers Presumptive TB registers	CaP TB Pediatric TB Form And/or TB screening logbooks/registers
Number and proportion of presumptive TB cases referred for lab-based TB diagnosis	TB screening logbooks/registers or Presumptive TB registers	CaP TB Pediatric TB Form And/or TB screening logbooks/registers, Presumptive TB registers
Number and proportion of pediatric (0-14 years) presumptive TB cases who are tested with Xpert	TB diagnostic logbooks/registers or Xpert logbooks/registers	CaP TB Pediatric TB Form And/or TB diagnostic logbooks/registers or Xpert logbooks/registers
Number and proportion of pediatric TB cases diagnosed with active TB disease among presumptive TB cases	Presumptive TB registers and TB registers	CaP TB Pediatric TB Form And/or TB registers/logbooks
Time between when a child is identified as a presumptive TB case and when the child is diagnosed with TB	Presumptive TB registers, TB registers/logbooks	CaP TB Pediatric TB Form And/or Presumptive TB registers, TB registers/logbooks
Number and proportion of pediatric TB cases started on DS-TB treatment	TB registers/logbooks	CaP TB Pediatric TB Form And/or TB registers/logbooks
Time between when a child is identified as a presumptive TB case and when the child is initiated on TB treatment	Presumptive TB registers, TB registers/logbooks	CaP TB Pediatric TB Form And/or

		Presumptive TB registers, TB registers/logbooks
Number and proportion of pediatric DS-TB cases who achieve treatment success	TB treatment register	TB treatment register
Number and proportion of all TB index cases for whom successful contact tracing has been done	TB registers/logbooks Contact tracing forms and registers if available	CaP TB Pediatric TB Form and TB register And/or TB registers/logbooks Contact tracing forms and registers if available
Number and proportion of pediatric household contacts who are negative to TB screening	TB registers/logbooks Contact tracing forms and registers if available	CaP TB Pediatric TB Form And/or TB registers/logbooks Contact tracing forms and registers if available

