Project data sample size: As this is a project evaluation, no specific sample size has been calculated. However, we estimate that the project will increase case detection by 2-fold and result in an additional 16,471 pediatric TB cases being treated.^{xxxix} This is based on an assessment of the number of children we project to screen (both HIV positive and HIV negative) in our project sites throughout the project. From the literature, we estimate that approximate Number Needed to Screen (NNS) to identify 1 TB case is 41 children. Assume that Number Needed to Screen (NNS) to identify 1 TB case is 41 (estimated NNS when symptom based screening is the only primary screening done)^{xl, xli}. Preventive treatment coverage is estimated to increase by four-fold, with an additional 52,317 children to be initiated on preventive therapy. This is based on the estimated number of child TB contacts we will identify through contact tracing plus HIV-infected children who qualify for preventative treatment.

To compare pre- and post-intervention outcomes, we will use either the ratio of the two proportions (relative risk) or the difference between the two proportions (risk difference). We will use Z-tests to assess the statistical significance of the estimated effect of CaP TB.

For measuring turn-around-time (TAT) between when a child is identified as a presumptive TB case and when the child is diagnosed with TB and the TAT between when a child is diagnosed as a presumptive TB case and when the child initiates TB treatment, if the TATs are approximately normally distributed, we will use the paired t-test to assess for statistical significance, otherwise we will use the Wilcoxon rank sum non-parametric test.

A. Quality Assurance

All data collectors will be trained in quantitative data collection by EGPAF staff. Prior to training, all data sources, abstraction and collection tools and procedures will be reviewed and tested. The HQ EGPAF team will provide on-going support to in-country teams throughout program implementation and all data collection activities.

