Aggregated data will not contain any identifiable information about clients and there is minimal potential for a breach in confidentiality. Additionally, patient level data abstracted for pre and post-intervention analysis will be aggregated for dissemination of findings to further protect confidentiality and will not contain any identifiable information about patients. The CaP TB Database Entry Tool will be located on a password-protected computer and/or Android device. The name of the patient and their caregiver, contact details and other identifiable information such as addresses, phone numbers will not be entered into the CaP TB Database Entry Tool at any time.

Only the health facility staff will have access to the identification number that links the ID to the patient's name and other identifiable patient information such as caregiver's name and address, TB Prevention therapy number, TB treatment number and patient identification numbers (if available) will be automatically encrypted before upload to the global database, so that upon review at headquarter level, an evaluation identification number is assigned to all children.

However, to protect the confidentiality of the patient, we will implement the following protective measures:

- a) At the country level, patient information, including the patient ID (if any) and treatment register numbers will be entered into the country CaP TB Database Entry Tool, and will be automatically encrypted, with the exception of DOB, before uploaded into the project database.
- b) The database with global data is housed in Microsoft cloud. The database developers, the Diagnostics Advisor and the Senior Strategic Information and Evaluation Officer and other key relevant staff such as the Senior Biostatistician responsible for data analysis, have access to all the country files, globally. These are the files that contain the patient IDs. Access to the database is password protected and access to this file can only be provided by the database developer.
- c) All calculations are done on the backend of the database system, including the count of unique number of patients; the dashboard which is the project's data visualization tool, presents aggregated data without patient IDs or treatment register numbers.
- d) The CaP TB Pediatric Form ID Number, generated by the project, will be made visible and will be used to track records with data quality errors.

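### At entry points using the ICF tool, the number of children screened is really a number of screenings, and no counting unit is set for the presumptive proportion

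*Combined protocol and SAP*

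**What the plan says.** - **Indicators.** Section II.B.1 lists the number and proportion of children screened among clinic attendees (item a). It then lists "Number and proportion of presumptive TB cases identified among children screened for TB" (item b, repeated as item f). Both are worded per child.
- **Screening tool.** Section VI says of the ICF tool: "This tool has no identifying information and will provide information on 1) number of children screened for TB". The tool also records entry point, sex, age, contact status, date, and "if the child has any signs of symptoms concerning for TB". Data collectors then "collate aggregated data using an ICF data abstraction tool".
- **Sources after launch.** Table 1 takes the screened count from "Pediatric TB Intensified Case Finding Screening Tools and Clinic attendance registers" and the presumptive count from the CaP TB Pediatric TB Form. Logbooks or registers are an alternative or additional source for both.
- **Pediatric TB Form.** Section VI says this form collects investigations "as well as treatment initiation information at patient level". The project's copy keeps the child ID where one exists, the treatment or preventive-therapy register number, sex and date of birth. Section X, item c, adds: "All calculations are done on the backend of the database system, including the count of unique number of patients".
- **Exceptions.** HIV clinics and community contact screening use the Pediatric TB Form, not the ICF tool, for every child screened. Countries that do not support the project tools use existing registers.
- **Other uses.** Section VII.A passes country totals of children screened to the cost-effectiveness analysis. Section IX plans on the basis that the "approximate Number Needed to Screen (NNS) to identify 1 TB case is 41 children".

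The text does not say that a child is screened or counted only once. It gives no de-duplication rule and no unit for item b.

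**The concern.** A child who attends outpatient, nutrition or MCH services several times may be screened each time. With no identifier and only aggregates in the database, each screen adds one to the total, and nothing collected allows a later correction. From the presumptive step onward, records can at least in part be linked to a child. The two sides of item b may therefore be in different units.

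Three things are at stake:

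- The reported number of children screened, in results and as a cost-effectiveness input, would be a number of screenings under the wrong label.
- The presumptive proportion could fall as a site screens more often, with no change in how many children are found.
- Section IX applies Z-tests to pre/post ratios or differences, so a change of unit between periods could be read as a programme effect.

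**Working it through.** **Is there a figure to reproduce?** No. The plan gives no presumptive proportion and no number of screens per child. The 16,471 additional cases cannot be rebuilt from the NNS of 41, because the projected number of children screened is not stated. Every value of m, s, p, q and n below is an assumption.

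**1. Overstatement of the count.** Let m be the mean number of screens per child on the ICF tool. Let s be the share of children screened on that tool, with the rest on the identified form and counted once. The reported count divided by children is s·m + (1 − s). With s = 1 this is m.

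**2. Item b with a de-duplicated numerator.** If the per-child proportion is p, the reported value is p / (s·m + 1 − s). With p = 5%:

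| m | s = 1: factor | s = 1: reads | s = 0.7: factor | s = 0.7: reads |
|---|---|---|---|---|
| 1 | 1.00 | 5.00% | 1.00 | 5.00% |
| 1.5 | 0.67 | 3.33% | 0.74 | 3.70% |
| 2 | 0.50 | 2.50% | 0.59 | 2.94% |
| 3 | 0.33 | 1.67% | 0.42 | 2.08% |

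**3. Item b when each screen has an independent chance q of being positive.** The per-child proportion is 1 − (1 − q)^m, the per-screening proportion is q, and the mixed ratio is [1 − (1 − q)^m] / m.

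- q = 5%, m = 2: per child 1 − 0.95² = 9.75%; per screening 5.00%; mixed 4.88%.
- q = 10%, m = 3: per child 1 − 0.9³ = 27.1%; per screening 10.0%; mixed 9.03%.

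The mixed ratio is again 1/m of the per-child value, but it lies close to the per-screening value.

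**4. Item b with forms counted and no de-duplication.** Each positive screen adds one to the numerator and each screen adds one to the denominator. The ratio is the per-screening proportion, with no mismatch.

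**5. Pre/post test, only if baseline counts children and the post-launch ratio is mixed.** Take p = 5% with no true change, n = 1,000 children per period, and an assumed two-sided alpha of 0.05 (the plan gives none). Compare 5% on n with 5%/m on n·m. The chance of a significant apparent fall is Φ[(d − 1.96·SE₀)/SE₁], where d is the difference, SE₀ the pooled and SE₁ the unpooled standard error. At m = 1.5, d = 0.0167, SE₀ = 0.0080 and SE₁ = 0.0083, giving 0.55. At m = 1.2 it is 0.15, and at m = 2 it is 0.93. If both periods use the same unit and m does not change, this effect is absent.

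**6. Screenings per case.** An NNS of 41 children corresponds to 41·m screenings: 61.5 at m = 1.5, 82 at m = 2 and 123 at m = 3.

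**The case against.** The strongest reply is that the mixed ratio is inferred, not documented. The unique-patient count is mentioned in the privacy section, which does not say which cascade step uses it. The child ID is recorded only where one exists, and register numbers arise only once therapy is started. Counting forms is equally consistent with the text, and item b is then coherent. This stands: a reader might infer that the presumptive proportion is necessarily diluted, and the documents do not establish that.

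Further points also stand:

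- **Pre/post bias.** A reader might infer that the item b comparison is biased downward. That needs baseline logbooks that count differently, or a change in repeat screening between periods. Section V.A shows that baseline extraction collects date of birth and any patient ID for linking registers. It does not say that screened children are de-duplicated, and it warns that some indicators will have no baseline data.
- **Item a as a proportion.** If attendance registers log attendances, both sides are already visits. Only the label of the count is wrong.
- **Scope.** HIV-clinic screening, community contact screening and register-only countries do not have this defect.
- **Consequences.** None of the four key indicators in section V.A uses the screened count. Observed NNS is not a listed indicator. The pre/post rates sent for cost-effectiveness are notifications and treatment or preventive-therapy starts, not screening.
- **Missing attachments.** The ICF tool and its abstraction form are not in the text, so a counting instruction there cannot be excluded.

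None of this changes the fact that, as described, the ICF tool cannot supply the per-child count that Table 1 assigns to it.

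**Conclusion.** The concern holds in a limited form. At ICF entry points the plan will report screenings as children screened, and this cannot be corrected afterwards. The overstatement there equals m. It is nil if no child is screened twice and twofold if children average two screens.

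For item b, the effect depends on an unstated rule. A de-duplicated numerator gives about 1/m of the per-child proportion (0.67, 0.50 and 0.33 at m = 1.5, 2 and 3). The dilution is smaller where some children are screened on the identified form: 0.74, 0.59 and 0.42 if 30% are. Counting forms gives no mismatch. Pre/post bias is a further conditional step, and the rejection rates in step 5 of the working apply only under that condition.

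The change should be made, because a primary-objective indicator and a cost-effectiveness input carry the wrong unit and the repair is cheap. It does not threaten the key impact indicators.

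**What to change.** 1. Label the ICF count as screenings in all results and in the cost-effectiveness input.
2. For item a at ICF entry points, report screenings over attendances.
3. For item b at ICF entry points, report positive screens over screenings. Take the numerator from the tool's symptom item, or from forms opened for a positive screen without de-duplication. The restriction to positive screens matters because section VI also opens forms for household contacts.
4. Apply the same unit to the baseline logbooks where they exist, and say where they cannot support it.
5. Report HIV-clinic and contact-tracing screening separately, with their own stated unit and a rule for children without an ID.
6. Do not set screenings per case against the planning figure of 41 children.

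The cost is mainly wording. If the abstraction form does not already total positive screens, it needs one more row; otherwise the form count can be used. The downside is that the headline becomes screenings, which is a less attractive figure than children.

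I would not add a recall question to identify first-time screens. It would miss screening at other facilities, it would help only if the numerator were de-duplicated too, and data collection ends in September 2021.

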After the child has a positive TB screen the appropriate healthcare worker, such as the treating clinician or TB nurse, will begin filling out their section designated for requesting health workers on the CaP TB Pediatric TB Form, pre-printed with sequential numbers in each country using the Form. For children screened at HIV clinics or during contact tracing, this section will be directly filled for all children screened, irrespective of the presence of signs or symptoms or TB. This part of the form contains identifying information of the pediatric patient, contact information and identifies if the patient is exhibiting sign or symptoms concerning of TB, and if so which ones. If signs or symptoms of TB are identified, the facility TB nurse or focal point will then detach the last copy of the form (the pink form) and keep this form at the facility. The remaining three carbonated copies of the CaP TB Pediatric TB form will then be used as a referral form for sample collection and TB testing. The patient or patient's caregiver will be sent with the remaining three copies of the carbonated form to have a specimen collected. The healthcare worker collecting the sample will then fill out the section "To be filled at specimen collection site." This section contains information on the date of collection and type of specimen collected. The remaining three copies of the carbonated form, along with the specimen will be sent to the laboratory for specimen processing. The laboratory staff will fill out the section "To be filled by lab personnel." This section will contain information about the type of testing performed, the date of testing and the results of testing. The laboratory staff will detach one copy (the blue form) and keep this at the laboratory. The remaining two copies of the CaP TB Pediatric TB form, which contains the patient's results, will then be returned to the requesting facility. The requesting facility/treatment unit will then complete the section "To be filled by TB treatment unit." This section will contain additional information, including results of chest X-ray and if the patient was diagnosed based on clinical symptoms with or without radiologic signs. This section will also contain information about treatment initiation or the facility to which the patient was referred for treatment initiation as well as the patient's TB treatment register number. The first (white) page will be kept at the requesting facility for their records.

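### Where the CaP TB Form supplies both numerator and denominator, 'presumptive cases referred' tends to 100% by design, so a rise over the register-based baseline may be partly or wholly an artefact

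*Combined protocol and SAP*

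**What the plan says.** Indicator c under the primary objective (section II.B.1, repeated in Table 1) is "Number and proportion of presumptive TB cases referred for lab-based TB diagnosis". The documents do not say what makes a case 'referred'. Secondary objective a compares the indicators with baseline in a subset of sites, and section IX plans a relative risk or risk difference with a Z-test.

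Section VI, under the use of project-specific tools, describes the workflow after launch. At most entry points the screening (ICF) tool records signs and symptoms first, and the Form comes only afterwards: "After the child has a positive TB screen the appropriate healthcare worker, such as the treating clinician or TB nurse, will begin filling out". In HIV clinics and contact tracing the Form is itself the screening tool, and "this section will be directly filled for all children screened, irrespective of the presence of signs or symptoms or TB". In either case, if signs or symptoms are found, one copy is detached and "The remaining three carbonated copies of the CaP TB Pediatric TB form will then be used as a referral form for sample collection" and testing. Then: "The patient or patient's caregiver will be sent with the remaining three copies of the carbonated form to have a specimen collected". A separate part of the Form is completed at specimen collection: "This section contains information on the date of collection and type of specimen collected".

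In Table 1 the post-launch source for both presumptive cases and referred cases is the Form and/or registers. The pre-intervention source for both is screening logbooks or presumptive TB registers. The table is presented as an example that may vary by country. Where the Form is not completed or not supported, section VI sends data collectors back to registers.

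**The concern.** A proportion is informative only if a child can be in the denominator without being in the numerator. For a child recorded on the Form with signs or symptoms, the described workflow leaves no such possibility: the Form that documents the presumptive case is also the referral slip. A presumptive child for whom no Form is started is not counted as a failure to refer. That child is missing from both terms, unless a register is used instead.

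The baseline is built differently, from registers. If the register proportion is below 100%, secondary objective a compares it with a value that is close to 100% because of how the Form is used. The error favours the programme, and the indicator would not show whether more children reached specimen collection.

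**Working it through.** The documents give no referral rate, target or sample size for this indicator, so there is no stated figure to reproduce. What follows is an illustration.

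**Inputs, all assumed.** *q* is the true referral proportion, the same before and after launch and correctly captured by registers. *f* is the share of post-launch presumptive cases sourced from the Form and counted as referred automatically.

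**Formulas.** Post-launch value = *f* × 1 + (1 − *f*) × *q*. Apparent risk difference = *f*(1 − *q*). Apparent relative risk = [*f* + (1 − *f*)*q*] / *q*. The true risk difference is 0 and the true relative risk is 1.

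| *f* | *q* | Post-launch value | Apparent risk difference | Apparent relative risk |
|---|---|---|---|---|
| 1.0 | 50% | 100% | +50 points | 2.00 |
| 1.0 | 70% | 100% | +30 points | 1.43 |
| 1.0 | 90% | 100% | +10 points | 1.11 |
| 0.8 | 50% | 90% | +40 points | 1.80 |
| 0.8 | 70% | 94% | +24 points | 1.34 |
| 0.8 | 90% | 98% | +8 points | 1.09 |
| 0.5 | 50% | 75% | +25 points | 1.50 |
| 0.5 | 70% | 85% | +15 points | 1.21 |
| 0.5 | 90% | 95% | +5 points | 1.06 |

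For example, *f* = 0.5 and *q* = 0.70 give 0.5 + 0.5 × 0.70 = 0.85, a rise of 15 points.

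**Chance that the Z-test calls this a gain.** I assume a two-sided 5% level (the plan states none), equal numbers per period and independent children. For *q* = 0.70, post-launch 0.85 and n = 100 per period:

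- pooled proportion 0.775; null standard error √(2 × 0.775 × 0.225 / 100) = 0.0591
- standard error under the alternative √[(0.70 × 0.30 + 0.85 × 0.15) / 100] = 0.0581
- (0.15 − 1.96 × 0.0591) / 0.0581 = 0.59, so the probability is 0.72

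For *q* = 50%, 70% and 90% at n = 100, the probabilities are 0.96, 0.72 and 0.27 with *f* = 0.5, and above 0.99, above 0.99 and 0.91 with *f* = 1.

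Table 3 expects at least 5 presumptive children per clinic. With 15–20 pilot sites in each of ten countries, that is 5 × 150 = 750 to 5 × 200 = 1,000 at baseline. The lowest probability among the same six combinations is then 0.96 at n = 750 and 0.99 at n = 1,000.

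**Effect of the denominator.** If the denominator were positive ICF screens, and 5%, 20% or 40% of them had no Form, the indicator would read 95%, 80% or 60%. The pull towards 100% comes from taking both terms from the Form.

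**The case against.** A reader might infer that indicator c is fixed at 100% after launch at every site and cannot register a change. The documents do not support that. Both Table 1 rows allow registers, the table is only an example, section VI prefers existing tools where they suffice, and some countries may not use the Form. Outside HIV clinics and contact tracing, the ICF tool records the positive screen before any Form exists, so a count that can exceed the number of Forms is collected. The Form's layout (Attachment C) is not in the documents, so a separate referral field cannot be excluded. The problem is also not an inability to show change: a rise may appear that cannot be interpreted.

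Nor need a rise be entirely an artefact. Sending a caregiver with a referral slip is a referral, and section IV.A.2 lists stronger referral systems as a project activity. Indicator d (tested with Xpert) would reveal part of any gap further down the cascade. Indicator c is not among the four key indicators in section V.A. The documents do not describe the baseline register columns, so a baseline below 100% is an assumption.

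These points limit the claim but do not remove it. Table 1 lists the ICF tool only for children screened, not for presumptive cases. Allowing either source without a rule for which governs gives the indicator different meanings across sites, and pooling dilutes the artefact without removing it. A real improvement in referral cannot be separated from the effect of the Form when 'referred' is undefined.

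**Conclusion.** The concern holds for Form-sourced data. There, indicator c tends towards 100% by design, and a pre/post rise against a register baseline may be partly or wholly an artefact. With an assumed unchanged true rate of 70%, the apparent rise is 30 points if all cases are Form-sourced and 15 points if half are. Over the assumed range (true rate 50–90%, Form share 0.5–1.0) it runs from 5 to 50 points.

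This rests on reading 'referred' as the Form having been issued, which the described workflow implies but no definition states. It also rests on a baseline rate and a Form-sourced share that the documents do not give. The four key impact indicators are not affected by this point.

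**What to change.** Amend II.B.1, Table 1 and section IX as follows.

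1. Report indicator c by data source (Form or register). Do not report or test a pre/post effect for 'referred' where the Form supplies both terms.
2. After launch, report the proportion of presumptive children with a specimen collection date on the Form. At entry points using the ICF tool, take the denominator from the aggregated positive ICF screens already collated, or from the presumptive register where one is kept. In HIV clinics and contact tracing, where the ICF tool is not used, the denominator can be Forms with signs or symptoms recorded, or again the register.
3. Compare specimen collection with baseline only at sites where the baseline presumptive register records a specimen or result, or can be linked to the laboratory or Xpert register. State the direction of bias. If the true baseline proportion is *s* and only a share *m* of collected specimens can be matched, the observed baseline is *s* × *m*, and the gain is overstated by *s*(1 − *m*).
4. If the Form has a separate referral field, define 'referred' by that field instead.

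The cost is mainly wording, since the specimen date and ICF counts are already collected. The post-launch value will look less favourable, and fewer sites will enter the pre/post comparison. The ICF tool carries no identifiers, so the ICF-based proportion is a ratio of aggregate counts, and its numerator must be limited to the same entry points and period.
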